3.2.10 Pre-existing conditions

3.2.10.1

Patients with a history of thromboembolism unrelated to a central line, or patients with a known predisposition syndrome for thromboembolism are not eligible.

3.2.10.2

Patients who have an uncontrolled or untreated infection are not eligible.

3.2.10.3

Patients with known overt cardiac disease, including but not limited to a history of myocardial infarction, severe or unstable angina, clinically significant peripheral vascular disease, Grade 2 or greater heart failure, or serious and inadequately controlled cardiac arrhythmia are not eligible.

3.2.10.4

Patients with a significant systemic illness that is not well-controlled in the opinion of the treating physician are not eligible.

REGULATORY

3.2.11

All patients and/or their parents or legal guardians must sign a written informed consent.

3.2.12

All institutional, FDA, and NCI requirements for human studies must be met.

4.0**TREATMENT PROGRAM**

Timing of protocol therapy administration, response assessment studies, and surgical interventions are based on schedules derived from the experimental design or on established standards of care. Minor unavoidable departures (up to 72 hours) from protocol directed therapy and/or disease evaluations (and up to 1 week for surgery) for valid clinical, patient and family logistical, or facility, procedure and/or anesthesia scheduling issues are acceptable per COG administrative Policy 5.14 (except where explicitly prohibited within the protocol).

4.1**Overview of Treatment Plan**

Upon enrollment, patients will be randomized to receive one of two treatments with lenalidomide; Regimen A (low dose) versus Regimen B (high dose). Please note there is a requirement for contraception for female patients of childbearing potential, such that they must commit to complete abstinence or agree to use two forms of effective contraception beginning at least 28 days prior to the first dose of lenalidomide and continuing until 28 days after the last dose of lenalidomide. (See [Section 3.2.9.4](#) and [Appendix II](#)). The primary study endpoint is objective response. Therapy may continue for a maximum of 26 cycles, in the absence of disease progression (see [Section 10.4](#) for definition) if off protocol criteria have not yet been satisfied (see [Section 8.1](#)).

Each cycle of therapy will last 28 days. Lenalidomide will be administered daily for the first 21 days of each cycle followed by a 7 day rest period. The lenalidomide dose for Regimen A will be 20 mg/m²/day by mouth daily and the dose for Regimen B will be 115 mg/m²/day by mouth daily. The dose will be rounded to within 10% of the prescribed dose for convenience of capsule size. The calculated dose should be rounded in a manner to minimize the daily number of capsules.

Patients or their guardians will keep a diary to document the intake of each dose of lenalidomide and potential side effects (see [Appendix VI](#)). Please instruct patient/parents to record each dose on the diary immediately rather than waiting until a later time. Errors on the diary should be crossed out and initialed. The patient diary should be reviewed with the patient and family at the completion of each treatment cycle, and drug should be accounted for at this time.

Brain MRI will be performed at baseline (within 1 week prior to study enrollment and \geq 1 week on a stable or decreasing dose of steroids for those patients receiving steroids) and prior to each odd-numbered cycle (ie, prior to cycles 3, 5, 7, 9, 11, and 13) for the first 13 cycles. During cycles 14-26, imaging will be performed prior to every third cycle (ie, prior to cycles 16, 19, 22, and 25), after cycle 26, and as clinically indicated. See [Section 14.0](#) for imaging requirements. Patients with spine disease will also have spine MRI performed at the same timepoints after enrollment, (ie, prior to cycles 3, 5, 7, 9, 11, and 13) for the first 13 cycles. During cycles 14-26, imaging will be performed prior to every third cycle (ie, prior to cycles 16, 19, 22, and 25), after cycle 26, and as clinically indicated.

Pharmacokinetic Study

For all patients, a blood sample must be obtained prior to the daily dose between Day 5-21 of cycle 1 at the time of routine safety lab monitoring. In the event of a dose reduction, a blood sample must also be obtained between Day 5-21 of the first cycle following each dose reduction. Please see [Section 13.1](#) for details on pharmacokinetic sample collection and shipping.

Required Pregnancy Testing During Study Participation

Pregnancy tests with a minimum sensitivity of 25 mIU/mL must be performed for female patients of childbearing potential, including those who commit to complete abstinence. If menstrual cycles are irregular, the pregnancy testing must occur weekly for the first 28 days and then every 14 days while on study, when the patient is taken off protocol therapy, and at Days 14 and 28 following the last dose of lenalidomide. All other female patients of childbearing potential must have pregnancy tests weekly for the first 28 days of study participation and then every 28 days while on study, at the time the patient is taken off protocol therapy, and at Day 28 following the last dose of lenalidomide. If pregnancy or a positive pregnancy test does occur during protocol therapy, lenalidomide must be immediately discontinued. Pregnancy testing and counseling must be performed if a patient misses her period, if her pregnancy test is positive, or if her menstrual bleeding is abnormal. Lenalidomide treatment must be discontinued during this evaluation.

Pregnancies and suspected pregnancies (including in the partner of a male study patient during study participation) must be reported as an adverse event. See [Section 11.0](#) for adverse event expedited reporting guidelines for pregnancies and suspected pregnancies.

Required Patient Education and Counseling

Counseling about pregnancy precautions and the potential risks of fetal exposure will be conducted every 28 days, on Day 1 of each cycle. See [Section 3.1.5.1](#) for counselor training requirements. Counseling must be completed prior to each dispensing of lenalidomide, and the counseling of each subject must be documented using the Lenalidomide Education and Counseling Guidance Document ([Appendix III](#)).

See [Section 7.1](#) for required observations prior to starting protocol therapy.

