3.2.2 Body Surface Area (BSA)

Patients must have a BSA ≥ 0.4 m² at the time of study enrollment.

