- confirmation of negative serum or urine pregnancy test (sensitivity of at least 25 mIU/mL) in female patients of childbearing potential,
- confirmation of the use of 2 forms of effective birth control for female patients of childbearing potential OR confirmation of commitment to complete abstinence, and
- completion and documentation of required lenalidomide education and counseling (all patients)

Dose calculations should be based on actual BSA and adjusted as necessary prior to each cycle. There is no maximum dosing.

Lenalidomide: PO once daily

Days: 1 through 21.

Dose: Regimen A (Low Dose): 20 mg/m²/dose (See [Appendix X](#) for Dosing Tables)
Regimen B (High Dose): 115 mg/m²/dose

Note: The calculated dose should be rounded to within 10% of the prescribed dose for convenience of capsule size. The calculated dose should be rounded in a manner to minimize the daily number of capsules. The dose should be given without food when possible, although this is not mandatory. If a patient vomits a dose within 10 minutes of administration and the capsules are clearly visible, the dose may be repeated. The capsules should be swallowed whole and not opened or chewed.

See [Section 5.0](#) for Dose Modifications based on Toxicities.

The therapy delivery maps (TDMs) for this cycle are on the next two pages. See [Section 4.3.1](#) for the Regimen A (Low Dose: 20 mg/m²/dose) therapy delivery map and [Section 4.3.2](#) for the Regimen B (High Dose: 115 mg/m²/dose) therapy delivery map.

Following completion of the first cycle, the lenalidomide cycle is repeated for up to a total of 26 cycles, as tolerated and in the absence of disease progression (see [Section 10.4](#) for Response Evaluation). If disease progression occurs, the patient will be taken off protocol therapy.

Susbequent lenalidomide cycles should begin on Day 29 or when ANC \geq 1,000/ μ L, platelet count \geq 100,000/ μ L (transfusion independent), whichever occurs later, AND once the following criteria have been met:

- confirmation of negative serum or urine pregnancy test (sensitivity of at least 25 mIU/mL),
- confirmation of the use of 2 effective methods of birth control for female patients of childbearing potential OR confirmation of commitment to complete abstinence,
- completion and documentation of required lenalidomide education and counseling (all patients).

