5.0 DOSE MODIFICATIONS FOR TOXICITIES

Lenalidomide dose reductions will not be re-escalated, even if there is minimal or no toxicity with the subsequent reduction in dose. Patients who experience significant toxicity (as listed in [Sections 5.1](#) and [5.2](#)) will have the dose reduced by 25% on subsequent cycles. Two dose reductions are allowed, as long as there is no evidence of disease progression (see [Section 10.0](#)). Each dose reduction will be a reduction of 25% of the starting dose; therefore the first dose reduction will be to 75% of the starting dose (either to 15 mg/m²/dose for patients on Regimen A or to 86 mg/m²/dose for patients on Regimen B), and a second reduction will be to 50% of the starting dose (either to 10 mg/m²/dose for patients on Regimen A or to 58 mg/m²/dose for patients on Regimen B). See [Appendix IX](#) for Regimen A dosing tables. Patients who again experience dose modifying toxicity after two dose reductions will be taken off protocol therapy.

If a dose reduction occurs, a blood sample for pharmacokinetic study should be drawn during the cycle subsequent to the reduction. See [Section 13.0](#) for details of pharmacokinetic sample collection.

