Male patients must agree to completely abstain from sexual contact with women who are pregnant or are able to become pregnant or use a latex condom every time he engages in sexual contact with women who are pregnant or who may become pregnant.

If a pregnancy occurs during treatment, the drug must be immediately discontinued and the suspected fetal exposure should be reported to CTEP via CTEP-AERS. Refer to [Section 11.9](#).

It is not known whether lenalidomide is excreted in human milk. Since many drugs are excreted in human milk and because of the potential for adverse reactions in nursing infants from lenalidomide, a decision should be made whether to discontinue nursing or to discontinue the drug, taking into consideration the importance of the drug to the mother.

Formulation and Stability:

Lenalidomide is available in 2.5 mg, 5 mg, and 25 mg capsules for oral administration for the purpose of this study. **Lenalidomide 10 mg capsules will not be used in this study.**

Each capsule contains lenalidomide as the active ingredient and the following inactive ingredients: lactose anhydrous, microcrystalline cellulose, croscarmellose sodium, and magnesium stearate. The capsules are supplied in tamper-evident, child-resistant, opaque,

high density polyethylene (HDPE) bottles) with polypropylene caps. Each bottle contains 100 capsules. Lenalidomide should be stored at 25°C (77°F); excursions permitted to 15-30°C (59-86°F).

Guidelines for Administration: See Treatment and Dose Modification sections of the protocol.

Each subject must receive counseling regarding the use and risks of lenalidomide by a healthcare professional who has received specific training by Celgene. Additional information about the training of these healthcare professionals can be found in [Section 3.1.5.1](#) and [Appendix I](#). The counseling of each subject must be documented using the Lenalidomide Education and Counseling Guidance Document ([Appendix III](#)). Once documentation has been confirmed, a pharmacist may dispense the investigational lenalidomide to the patient. Pharmacists may only dispense up to a 28-day supply at one time (1 cycle, or a 21-day supply for the purpose of this study). A Lenalidomide information sheet ([Appendix V](#)) must be provided each and every time the medication is dispensed. Prescriptions may not be mailed to the patient.

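### Appendix IX, 10 mg/m² table: the 7.5/10 mg boundary at BSA 0.82/0.83 is misplaced and should be 0.87/0.88 (minor)

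*Combined protocol and SAP*

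**What the plan says.** Section 4.1 states the rule: "The dose will be rounded to within 10% of the prescribed dose for convenience of capsule size". Section 4.3 repeats it: "The calculated dose should be rounded to within 10% of the prescribed dose for convenience of capsule size". Both sections also ask for as few capsules per day as possible.

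The drug information in Section 6.1 fixes the step size: "Lenalidomide is available in 2.5 mg, 5 mg, and 25 mg capsules for oral administration for the purpose of this study". It adds that 10 mg capsules are not used. Section 4.3 rules out part-capsules: "The capsules should be swallowed whole and not opened or chewed". Every dose is therefore a whole multiple of 2.5 mg.

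Section 5.0 defines when the 10 mg/m² table applies: "a second reduction will be to 50% of the starting dose (either to 10 mg/m²/dose for patients on Regimen A". It is the last dose level: "Patients who again experience dose modifying toxicity after two dose reductions will be taken off protocol therapy".

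The Appendix IX table for 10 mg/m² gives 5 mg for BSA 0.44–0.62, 7.5 mg for 0.63–0.82, 10 mg for 0.83–1.12 and 12.5 mg for 1.13–1.37, and continues upward in 2.5 mg steps. Appendix IX states rounding to the nearest 2.5 mg in words only for BSA of 2.20 m² or more.

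**The concern.** The 10 mg row of this table covers 0.30 m² (0.83–1.12) and the 7.5 mg row only 0.20 m² (0.63–0.82). At 10 mg/m² a 2.5 mg step corresponds to 0.25 m², so two neighbouring rows of 0.20 and 0.30 m² suggest that their shared boundary has slipped. If so, children just above it receive the larger dose when the smaller is closer to what was prescribed. They would do so at the level reached only after two reductions for toxicity. What is at stake is a dosing entry and its agreement with the rounding rule; the statistical conclusions of the trial are not.

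**Working it through.** **Inputs.** Dose level 10 mg/m² (Section 5.0); 2.5 mg steps (Sections 6.1 and 4.3); tolerance ±10% (Sections 4.1 and 4.3); row limits from Appendix IX.

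**Step 1: do the boundaries follow a rule?** Under nearest-2.5-mg rounding, the boundary between doses d1 and d2 is (d1 + d2)/2 ÷ 10.

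| Doses (mg) | Computed boundary (m²) | Table rows meet at | Offset (m²) |
|---|---|---|---|
| 5 / 7.5 | 0.625 | 0.62/0.63 | 0 |
| 7.5 / 10 | 0.875 | 0.82/0.83 | −0.05 |
| 10 / 12.5 | 1.125 | 1.12/1.13 | 0 |
| 12.5 / 15 | 1.375 | 1.37/1.38 | 0 |
| 15 / 17.5 | 1.625 | 1.62/1.63 | 0 |
| 17.5 / 20 | 1.875 | 1.87/1.88 | 0 |
| 20 / 22.5 | 2.125 | 2.12/2.13 | 0 |

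Six of seven reproduce exactly. A geometric midpoint for the second boundary, √(7.5 × 10)/10 = 0.866, does not give 0.825 either.

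**Step 2: size of the deviation.** Deviation = dose ÷ (10 × BSA) − 1.

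| BSA (m²) | Prescribed (mg) | Table: 10 mg | Alternative: 7.5 mg |
|---|---|---|---|
| 0.83 | 8.3 | +20.5% | −9.6% |
| 0.84 | 8.4 | +19.0% | −10.7% |
| 0.85 | 8.5 | +17.6% | −11.8% |
| 0.86 | 8.6 | +16.3% | −12.8% |
| 0.87 | 8.7 | +14.9% | −13.8% |

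At all five values 7.5 mg is closer. Only at 0.83 does it also satisfy the 10% rule; at 0.84–0.87 neither step does.

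**Step 3: capsule count.** 7.5 mg = 5 + 2.5 and 10 mg = 5 + 5: two capsules each. The instruction to minimise capsules does not favour 10 mg.

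**Step 4: all three Regimen A tables.** On a 0.01 m² grid, 36 of 530 tabulated values deviate by more than 10%: 3 at 20 mg/m², 8 at 15 mg/m² and 25 at 10 mg/m². At 35 of them no multiple of 2.5 mg is within 10%; the exception is 10 mg/m² at BSA 0.83. At 29 of the 36 the table already gives the nearest step. The other seven are the five values above and two at 15 mg/m².

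**Step 5: the two values at 15 mg/m².** The 7.5/10 mg boundary computes to 8.75 ÷ 15 = 0.583; the rows meet at 0.56/0.57. At BSA 0.57 and 0.58 the table gives 10 mg (+17.0%, +14.9%) where 7.5 mg would be −12.3% and −13.8%. Neither step is within 10%.

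**Step 6: reduction relative to the doses actually given.** With BSA unchanged, a child at 0.83–0.87 starts on 17.5 mg (row 0.82–0.93) and first reduces to 12.5 mg (row 0.76–0.91). The second reduction to 10 mg leaves 10/17.5 = 57.1% of the starting dose; to 7.5 mg it leaves 7.5/17.5 = 42.9%. Each is 7.1 points from 50%. The last step is a 20% fall (12.5 to 10) or a 40% fall (12.5 to 7.5), against a nominal 33% (15 to 10 mg/m²).

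**The case against.** **The boundary may be deliberate.** It lies near the BSA at which 7.5 mg becomes more than 10% too low: 7.5 ÷ (0.9 × 10) = 0.833. The author may have capped under-dosing there. This fails on two counts. Such a cap would keep BSA 0.83 on 7.5 mg, since −9.6% is within the limit. It would also move the 5/7.5 mg boundary to 5 ÷ 9 = 0.556, whereas the table keeps 5 mg up to 0.62, where the dose is 19.4% low.

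**Nearest-2.5-mg rounding is not stated for these rows.** This stands: it is inferred from the other six boundaries. Only the entry at BSA 0.83 conflicts with a written rule that could have been met.

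**No harm is shown.** This also stands. A reader might infer that children who have already had toxicity are dangerously overdosed. But 10 mg at BSA 0.83 is 12.0 mg/m², below the 15 mg/m² of the first reduction and below the lowest dose in the paediatric CNS Phase I study described in Section 2.4, which reached no MTD. Measured against the actual 17.5 mg starting dose, the correction is no closer to 50% than the present entry.

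**A wider reading: the 10% rule lacks a fallback.** A reader might infer from the 35 unattainable values that prescribers are left without a dose. The documents do not support that. Appendix IX supplies a dose for every BSA from 0.44 m² upward, and the Regimen A delivery map (Section 4.3.1) and Section 5.0 refer to it. Eligible patients at BSA 0.40–0.43 have no row, but a sentence saying that the table governs would not help them.

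**Conclusion.** The 0.82/0.83 boundary in the 10 mg/m² table is wrong as written. Five grid values (BSA 0.83–0.87) carry 10 mg where 7.5 mg is nearer, and one of them (0.83) breaks the 10% rule when a compliant dose exists. The conclusion assumes that the table was meant to follow nearest-2.5-mg rounding, as its other six boundaries do.

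The impact is minor. It reaches only Regimen A patients who have had two dose reductions and whose BSA falls in a 0.05 m² window. The documents give no BSA distribution, so the number of such patients cannot be computed. Sample size, power, the response endpoint and the stopping rules are untouched.

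The count of 36 values beyond 10% should not be read as 36 table errors: 29 are already the best available step. The two values at 15 mg/m² are a matter of consistency, because no attainable rule is broken there.

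**What to change.** In the Appendix IX table for 10 mg/m² (Dose Level -2), change the two rows to **0.63–0.87: 7.5 mg** and **0.88–1.12: 10 mg**. Values beyond 10% then fall from 36 to 35, and the largest deviation from 20.5% to 19.4% (BSA 0.62); what remains is set by the capsule strengths.

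Optionally, for consistency, move the 7.5/10 mg boundary of the 15 mg/m² table from 0.56/0.57 to 0.58/0.59.

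If the present boundary was intended, one line in Appendix IX giving the reason would do instead. The cost is one shared row limit, or two with the optional change; no analysis or procedure needs to be altered.

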4.2 Concomitant therapy restrictions

4.2.1

Concurrent cancer therapy, including chemotherapy, radiation therapy, immunotherapy, or biologic therapy may NOT be administered to patients while on this study. The use of alternative or complementary therapies is discouraged.

4.2.2

Radiotherapy is not permitted.

4.2.3

Filgrastim (G-CSF) may be used at the treating physician's discretion in patients with severe neutropenia (i.e. ANC <500/ μ L) to enhance neutrophil recovery when clinically indicated (for culture proven bacteremia or invasive fungal infections). Prophylactic or routine use of filgrastim in clinically well patients awaiting count recovery is not recommended.

4.2.4

Corticosteroid therapy is permissible only for the treatment of increased intracranial pressure or physiologic replacement. The lowest dose consistent with good medical management should be used. Corticosteroids should NOT be used as an antiemetic due to their effect on the blood brain barrier. Patients on steroids who require an increase in steroid dose for worsening neurologic symptoms should have an MRI performed within 72 hours to rule out tumor progression.

4.2.5

Appropriate antibiotics, blood products, antiemetics, fluids, electrolytes and general supportive care are to be used as necessary. Antiemetics should not be given prophylactically for cycle 1.

4.2.6

Anticonvulsants may be administered as clinically indicated. However, it is unclear what effect, if any, lenalidomide has on anticonvulsant pharmacokinetics. It is strongly recommended that anticonvulsant levels be checked at least weekly during the first course of therapy.

4.2.7

Drugs known to be pro-thrombotic (i.e. erythropoietic stimulating agents) should be avoided.

For COG Supportive Care Guidelines see:

https://members.childrensoncologygroup.org/prot/reference_materials.asp under Standard Sections for Protocols.

4.3

Lenalidomide Administration

The lenalidomide cycle will be repeated every 28 days. Each cycle will be comprised of lenalidomide orally once daily for 21 days followed by 7 days without lenalidomide. Lenalidomide should be taken at approximately the same time each day. One cycle of lenalidomide is described below. **Lenalinomide is distributed by the NCI DTCD. Do not use commercially available drug.**

Begin Cycle 1 on Day 1 if ANC \geq 1,000/ μ L, platelet count \geq 100,000/ μ L (transfusion independent), and upon the following:

- confirmation of negative serum or urine pregnancy test (sensitivity of at least 25 mIU/mL) in female patients of childbearing potential,
- confirmation of the use of 2 forms of effective birth control for female patients of childbearing potential OR confirmation of commitment to complete abstinence, and
- completion and documentation of required lenalidomide education and counseling (all patients)

Dose calculations should be based on actual BSA and adjusted as necessary prior to each cycle. There is no maximum dosing.

Lenalidomide: PO once daily

Days: 1 through 21.

Dose: Regimen A (Low Dose): 20 mg/m²/dose (See [Appendix X](#) for Dosing Tables)
Regimen B (High Dose): 115 mg/m²/dose

Note: The calculated dose should be rounded to within 10% of the prescribed dose for convenience of capsule size. The calculated dose should be rounded in a manner to minimize the daily number of capsules. The dose should be given without food when possible, although this is not mandatory. If a patient vomits a dose within 10 minutes of administration and the capsules are clearly visible, the dose may be repeated. The capsules should be swallowed whole and not opened or chewed.

See [Section 5.0](#) for Dose Modifications based on Toxicities.

The therapy delivery maps (TDMs) for this cycle are on the next two pages. See [Section 4.3.1](#) for the Regimen A (Low Dose: 20 mg/m²/dose) therapy delivery map and [Section 4.3.2](#) for the Regimen B (High Dose: 115 mg/m²/dose) therapy delivery map.

Following completion of the first cycle, the lenalidomide cycle is repeated for up to a total of 26 cycles, as tolerated and in the absence of disease progression (see [Section 10.4](#) for Response Evaluation). If disease progression occurs, the patient will be taken off protocol therapy.

Susbequent lenalidomide cycles should begin on Day 29 or when ANC \geq 1,000/ μ L, platelet count \geq 100,000/ μ L (transfusion independent), whichever occurs later, AND once the following criteria have been met:

- confirmation of negative serum or urine pregnancy test (sensitivity of at least 25 mIU/mL),
- confirmation of the use of 2 effective methods of birth control for female patients of childbearing potential OR confirmation of commitment to complete abstinence,
- completion and documentation of required lenalidomide education and counseling (all patients).

